- An anthracycline; either daunorubicin , idarubicin or mitoxantrone at standard doses daily for 3 days, starting on day 1.

The second induction will consist of dose-adjusted high dose Ara-C alone (1-1.5grm/m² Q12 hrs on day 1, 3, and 5, per standard of care). The timing for initiation of the second induction depends upon results of marrow done 14-21 days after the first induction according to standard of care practice.

- Patients who do not achieve remission at the conclusion of 2 inductions will be considered screen failures and offered alternative therapies.

Consolidation:

- Omacetaxine 1.25 mg/m² sub-cutaneously twice daily for 5 consecutive days every 28 (\pm 8) days for a total of 3 cycles.

Maintenance:

- Subjects in continuous remission after 3 cycles of consolidation with omacetaxine will receive maintenance omacetaxine 1.25mg/m² twice daily for 3days, every 28 days, for up to 6 cycles.

Sample size and patient selection:

- **Screening:** 45 patients with newly diagnosed, untreated AML eligible for induction chemotherapy. Patients who received 1-2 cycles of hypomethylating therapy for cytoreduction are also eligible.
- **Consolidation/maintenance:** 15 patients in first complete remission after 2 inductions.

Assessment of response:

- Bone marrow biopsy and aspirate will be obtained at day 14-21 of the 1st cycle, and at day 28 or at count recovery, whichever occurs first.
- Prior to each consolidation cycle, responses will be evaluated with a complete blood count (CBC) and bone marrow aspiration/biopsy to document continued remission.
- Bone marrow aspirate to confirm continuous remission will be obtained every 3 months during maintenance, and as clinically indicated thereafter.

Statistical Methods:

- This study is an open label, pilot study. Continuous data will be described using descriptive statistics (n, mean, median, minimum, and maximum) while discrete data will be described using frequency counts and percentages.

Time line: 2-3 years, based on previous accrual in the target population.

1. BACKGROUND:

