High dose cytarabine (HiDAC, doses $> 1.5 \text{ g/m}^2/\text{d}$) administered during induction results in improved recurrence-free and overall survival in younger AML patients < 60 ,¹² but is associated with increased toxicities in older patients^{13,14}. We have recently reported on the safety and efficacy of modified HiDAC induction for newly diagnosed patients ≥ 60 with AML ([name] et al. ASCO 2010). HiDAC induction was well-tolerated, associated with high CR rates (69%), and comparable early mortality to standard dose cytarabine induction (19%). In our series, 37/59 (63%) patients were able to receive the 2 planned inductions. Of the 41/59 (69%) that achieved remission, 6, 11, and 10 patients received 1, 2, and 3 consolidations with HiDAC, respectively. **However, despite high initial CR rate (69%) and the delivery of standard consolidation in 80%, the median relapse-free survival was 11 months, and most patients died from relapsed leukemia.** Therefore, exploring alternative consolidation regimens is desirable. Since the current study opened, we have learned that prospectively, our patients did not tolerate the 2 consecutive cycles of modified HiDAC/daunorubicin due to cardiac toxicity, and have amended the protocol to limit induction to only 1 cycle of standard infusional cytarabine $100\text{mg}/\text{m}^2$ over 24hrs. daily $\times 7$ days and an anthracycline (daunorubicin, idarubicin, or mitoxantrone at standard doses). At count recovery or sooner if residual leukemia is present at the end of induction, 1 cycle of dose-adjusted high dose cytarabine can be administered (1-1.5gm/m² IV Q12hrs. on days 1,3, and 5, per standard of care).

1.3 Consolidation Therapy for Older Patients with AML.

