1.6 Rationale for the study

The outcome of older patients with AML is dismal with standard anti-leukemic chemotherapy, and only a minority of those patients can proceed with curative allogeneic stem cell transplantation. Despite good initial responses (CR 50-70%) with anti-leukemic induction chemotherapy, half of all patients will relapse within a year and 80% would have relapsed by 2 years. Therefore, alternative consolidations are needed. Given that omacetaxine is an active anti-leukemic agent that is well tolerated, we propose to conduct a prospective pilot study exploring safety and tolerability of omacetaxine to treat minimal residual disease in the form of consolidation and maintenance for patients age 55 and older with newly diagnosed AML in first complete remission. **This trial is a necessary step for an efficacy phase II trial.**

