 - **Complete Remission (CR):** Normocellular marrow with < 5% blasts, absence of auer rods and of any unique phenotype identical to what was found in the pretreatment specimen, with ANC $\geq 1 \times 10^9/L$ and platelet count $\geq 100 \times 10^9/L$, and transfusion independence, as well as no residual evidence of extramedullary AML.
 - **Complete Response with incomplete blood count recovery (CRi):** Meets criteria for CR above, except for residual neutropenia (ANC < $1 \times 10^9/L$) or thrombocytopenia (platelets < $100 \times 10^9/L$)
 - **Complete Response with incomplete platelet recovery (CRp):** Meets criteria for CR above, but platelets are < $100 \times 10^9/L$.
 - **Cytogenetic Complete Remission (CRc):** Disappearance of cytogenetic abnormalities thought to be associated with the AML.
 - **Molecular Complete Remission (CRm):** Disappearance of molecular abnormalities thought to be related to the AML.
 - **Treatment failure:**
 - **Resistant disease:** Patient survives ≥ 7 days post-chemotherapy and has persistent AML in blood or bone marrow.
 - **Aplasia:** Patient survives ≥ 7 days post-chemotherapy, but dies while cytopenic, with an aplastic bone marrow.
 - **Morphologic relapse:** Reappearance of blasts post-chemotherapy in peripheral blood or bone marrow.
 - **Molecular/cytogenetic relapse:** Reappearance of molecular or cytogenetic abnormality.
 - **Clearance of Leukemia at the day 14 marrow:** < 5% blasts in a hypocellular marrow (<15% cellularity).

- **Overall survival (OS):** Time from entry onto trial until death from any cause.
- **Relapse free survival (RFS):** Time from Remission (CR, CRi, CRp) until disease relapse or death from any cause.
- **Event free survival (EFS):** Time from entry onto trial to treatment failure/relapsed disease, or death from any cause.
- **Remission duration:** Time from date of CR (or CRp, CRi) until disease relapse.

3.3.3 Safety Assessment and Study Tests:

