Toxicities will be monitored by history, physical examination, and laboratory monitoring (CBC, serum chemistries to include renal and liver function tests) weekly during consolidation and monthly during maintenance according to standard of care (Appendices D-F). Toxicity will be assessed according to the NCI Common Toxicity Criteria Version 4.0 (available at the NCI web site <http://ctep.cancer.gov/reporting/ctc.html>). Adverse events will be monitored on an ongoing basis. No AEs will be collected during the screening period (the time from diagnosis to completion of the standard of care inductions).

3.3.4 Dose Modifications and Stopping Rules:

A. Omacetaxine

- ***Hematological toxicity:***

- The following table summarizes dose adjustments for hematological toxicity during consolidation and maintenance with Omacetaxine and are based on time to count recovery to < grade 2 hematological toxicity. Hematologic toxicity only refers to WBC/neutrophils and platelets and not hemoglobin/hematocrit, given that anemia is expected and may not resolve after chemotherapy regardless of AML-status. Dose-reductions and delays do not apply to anemia.

Time to resolution to < grade 2 hematologic toxicity (days)	Action 1	Action 2: Hematologic toxicity after 1 st dose reduction
≤ 36	No dose reduction	No dose reduction
> 36 and < 50	20% dose reduction, i.e. omacetaxine 1.25 mg/m ² sub-cutaneously twice daily for 4 days during consolidation, or 1.25mg/m ² twice daily for 3 days during maintenance	Additional 25% dose reduction, i.e. omacetaxine 1.25 mg/m ² sub-cutaneously twice daily for 3 days during consolidation, or 1.25mg/m ² twice daily for 2 days during maintenance
> 50	Perform bone marrow aspirate and biopsy. If relapse – patient will be taken off study. If hypoplastic marrow (cellularity < 10%), reassess after 2 weeks. If recovery achieved within 2 weeks post-marrow assessment, resume omacetaxine after 60% dose reduction; i.e. omacetaxine 1.25 mg/m ² sub-cutaneously twice daily for 3 days during consolidation, or 1.25mg/m ² twice daily for 2 days during maintenance If no recovery 2 weeks post-marrow assessment, patient will be taken off study.	No further dose reduction. Patient will be taken off study

- ***Non-hematological toxicity:***

- Patient with grade III-IV non-hematological toxicity (deemed at least “possibly” related to omacetaxine) will have study drug held until toxicity has recovered to grade 1 or less. Treatment may resume after 20% dose reduction.

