Data quality will be monitored on an ongoing basis by random checks of CRFs following the Leukemia Working Group meetings. Co-investigators and staff will be trained on the conduct of the protocol and any additional training based on protocol amendments at the Hematology/Leukemia multi-disciplinary meetings, which meets regularly. Recording, grading, and reporting of adverse events will be carried out contemporaneously with each patient's clinic visit and will abide by the guidelines provided by the Winship Cancer Institute Clinical Trials Office. Deviations will be added to the Deviation Log, which is updated and reviewed at the Leukemia Working Group meetings.

The Principal investigator is responsible for sending a yearly IND summary report, which includes an update and status of the study and a tabulation of the AEs/ SAEs, as well as status of the study subjects, to the FDA. The PI is also responsible for collecting, reviewing, analyzing and reporting to the FDA and other investigators any potential serious risks that qualify for reporting under the FDA's IND Safety Reporting regulations at 21 CFR §312.32, .64 and 21 CFR § 320.31. In addition, the Sponsor-Investigator must copy the Emory IRB on

any such reports and include an analysis of whether the Sponsor-Investigator believes the event constitutes an Unanticipated Problem Involving Risks to Subjects or Others.

6. STATISTICAL CONSIDERATIONS:

Safety: Target omacetaxine dose is the dose that can be delivered to 70% patients without dose limiting toxicity (DLT) as defined above (section 3.3.4). Safety analysis will be conducted through continuous monitoring of AE/SAE. If 2 of the first 3 patients experience DLT, we stop the trial. After that, we stop the trial if there is evidence that the target probability of DLT exceeds 30% and the probability of falsely stopping the trial is 10% or less. The following table gives the minimum number of DLTs in order to stop the trial and the probability of falsely terminating the trial if in fact the probability of DLT is 30% calculated using the binomial distribution. For example, if after enrolling 6 patients, 4 or more experienced DLT, then we stop the trial and conclude that the target probability of DLT is more than 30%. The probability of incorrectly stopping the trial is 0.07.

To be considered safe, the upper limit of the one-sided 95% CI of DLT among 15 patients must not be greater than 30%.

Number of Patients	3	4	5	6	7	8	9	10	11	12	13	14	15

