Number of DLTs to Stop Trial	> 1	> 1	> 3	> 3	> 4	> 4	> 4	> 5	> 5	> 6	> 6	> 6	> 7
Probability of falsely terminating the trial		0.08	0.03	0.07	0.03	0.06	0.10	0.05	0.08	0.04	0.07	0.10	0.05

Feasibility: Feasibility is defined as delivery of 9 cycles of therapy for at least 2/3 of the patients. The proportion of patients with full treatment delivery will be estimated with an exact 95% confidence interval.

Futility: Based on our previous data showing a median relapse-free survival of 13.8 months, we will consider our consolidation/maintenance regimen futile if $\geq 80\%$ of those entering in CR relapse during consolidation/maintenance.

Kaplan-Meier curves will be used to estimate the distribution of time to relapse, relapse free survival, and overall survival.

Analysis of survival outcomes (OS, EFS, RFS) for patients who undergo transplantation in CR will include censoring and no censoring at the time of transplantation.

References:

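### The futility trigger of 80% relapse during treatment does not follow from the 13.8-month median RFS it is said to rest on, and its trigger probabilities are not stated

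*Combined protocol and SAP*

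**What the plan says.** The futility paragraph of Section 6 reads: "Based on our previous data showing a median relapse-free survival of 13.8 months, we will consider our consolidation/maintenance regimen futile if" 80% or more "of those entering in CR relapse during consolidation/maintenance". It gives no derivation, no interim look, no stopping action and no probability of meeting the rule.

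Other places that bear on it:

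- **Length of treatment.** The Synopsis and Section 3.3.1 plan three consolidation cycles every 28 (±8) days, then maintenance "twice daily for 3days, every 28 days, for up to 6 cycles". The feasibility paragraph of Section 6 counts nine cycles.
- **Endpoint.** Section 3.3.2 defines RFS as "Time from Remission (CR, CRi, CRp) until disease relapse or death from any cause". The futility trigger counts relapse only.
- **Other historical figures.** Section 1.2 says of the group's own series that "the median relapse-free survival was 11 months, and most patients died from relapsed leukemia". Section 1.6 says of older patients that "half of all patients will relapse within a year and 80% would have relapsed by 2 years".
- **The DLT rule in the same section.** It does report operating characteristics: "The following table gives the minimum number of DLTs in order to stop the trial and the probability of falsely terminating the trial".

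**The concern.** A reader would take the 80% as a threshold worked out from the 13.8-month benchmark. If it were, a result below 80% would say something about performance against that benchmark. But the counting period ends well before 13.8 months, when fewer than half of patients at the benchmark would be expected to have relapsed or died. The trigger therefore lies far above what the benchmark implies, and the plan does not say how far.

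The rule is the only criterion in Section 6 aimed at disease control alone, and Section 1.6 presents the trial as a step towards an efficacy phase II study. A not-futile result could be carried forward as though it had been judged against 13.8 months.

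**Working it through.** **Inputs.** Benchmark median RFS 13.8 months and trigger of at least 80% (Section 6); 15 patients, three cycles of 28 (±8) days and up to six of 28 days (Synopsis); 11 months (Section 1.2); 50% relapse within one year and 80% by two years (Section 1.6). Assumptions: 30.4375 days per month, independent patients, all 15 in the denominator, and exponential RFS unless stated.

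**Step 1. Method check.** The plan shows no calculation for the 80%, so there is nothing to reproduce there. For the DLT rule, the binomial probability of 4 or more of 6 at 30% is 0.0705, against the plan's 0.07.

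**Step 2. Trigger and window.** 0.80 × 15 = 12 patients. Planned treatment is 9 × 28 = 252 days, and 252 / 30.4375 = 8.28 months. At the longest scheduled spacing it is 3 × 36 + 6 × 28 = 276 days, or 9.07 months.

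**Step 3. Bound that needs no curve.** Let F be the cumulative event probability from remission, L the gap from remission to consolidation and t the window. The share with an event on treatment, among those still in remission at its start, is (F(L+t) − F(L)) / (1 − F(L)). This cannot exceed F(L+t), which is at most 0.5 while L + t ≤ 13.8 months. So the bound holds for gaps up to 13.8 − 8.28 = 5.5 months (252 days) or 13.8 − 9.07 = 4.7 months (276 days). At 0.5, P(12 or more of 15) = 576 / 32768 = 1.8%.

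**Step 4. Exponential RFS.** Share p = 1 − 2^(−t/median); trigger probability = P(Binomial(15, p) ≥ 12).

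| True median (months) | p, day 252 | P(trigger) | p, day 276 | P(trigger) |
|---|---|---|---|---|
| 13.8 | 0.340 | 0.04% | 0.366 | 0.08% |
| 11 | 0.406 | 0.2% | 0.435 | 0.5% |
| 6.9 (half) | 0.565 | 5% | 0.598 | 9% |
| 4.6 (one third) | 0.713 | 34% | 0.745 | 44% |

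At a 13.8-month median, 80% is reached only at 13.8 × ln 5 / ln 2 = 32 months. For 80% by day 252 the median would have to be 8.28 × ln 2 / ln 5 = 3.6 months.

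**Step 5. Section 1.6 figures.** A Weibull curve through 50% at 12 months and 80% at 24 months has shape log2(ln 5 / ln 2) = 1.215. It gives 36% by day 252 and a trigger probability of 0.06%. Section 1.6 reaches 80% at two years, about three times the planned treatment length.

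**Step 6. Sensitivity, day 252.** At 13.8 months, Weibull shapes 0.5 to 2 give shares of 22% to 42% and trigger probabilities of at most 0.3%. At 6.9 months, shapes 0.7 to 1.5 with a gap of 0 to 2 months give 1% to 25%. If 10% to 20% of RFS events were deaths without relapse (assumption), the relapse-only trigger probability at 6.9 months falls from 5% to between 0.7% and 2%.

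**The case against.** **A lenient floor may be intended.** A futility limit is meant to lie far from the benchmark, and based on need not mean calculated from. Reaching the two-year relapse figure of Section 1.6 while still on treatment would be a poor result by any standard. This reading is possible, so the 80% cannot be called an arithmetical error. But the plan does not state it, and it leaves the claimed basis in 13.8 months unexplained.

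**Feasibility would catch a poor regimen.** This largely stands. Section 3.3.4 discontinues omacetaxine for recurrent leukemia, and feasibility requires nine cycles in at least 10 of 15 patients, so six relapses or deaths before completion are enough to fail it. On the Step 4 assumptions, P(6 or more of 15) by day 252 is about 94% at a 6.9-month median. (This is slightly too high, since events after the last dose of cycle nine do not count.) A reader might infer that a regimen with half the benchmark median would pass Section 6 unflagged; the documents do not support that. Feasibility does not isolate disease control, however. It also counts toxicity and withdrawal, and would fail about 40% of the time from relapse or death alone at 13.8 months.

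**The rule does have a window.** It names the treatment phase, so it would be wrong to say there is none. What is missing is a fixed length in days. Nor should the dependence on delays be overdrawn. If all nine cycles took 36 days, the longest recovery time without dose reduction in the Section 3.3.4 table, treatment would last 324 days and the trigger probability at 6.9 months would be 19%. That is an extreme: the ±8 days is given for consolidation only, and at 276 days the figure is 9%.

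**The DLT comparison is not like for like.** The DLT rule stops the trial; the futility sentence states only a conclusion. That weakens the parallel but does not remove the need to know how the rule behaves.

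**The two medians may come from different data.** Section 1.2 describes patients aged 60 and over, and the source of 13.8 months is not given. A reader might call 13.8 and 11 a contradiction; the documents support only a request to reconcile them.

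**Conclusion.** The concern holds. At a 13.8-month median, no more than half of patients can have an event within either scheduled window, and that needs no assumption about curve shape provided consolidation starts within about 4.7 months of remission. The trigger of 80% therefore does not follow from the stated basis. Under exponential RFS, a regimen with half the benchmark median would be called not futile about 95% of the time at day 252 and 91% at day 276.

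The rule is not incapable of triggering: at a median of 4.6 months it does so in 34% to 44% of trials. The figures at worse medians depend on the assumed curve and gap, as Step 6 shows. The relapse-only count makes the rule less sensitive still.

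Severity is minor to moderate. Safety and tolerability are the primary objectives, the futility rule carries no stated stopping action, Kaplan-Meier curves for RFS are planned, and the feasibility rule gives partial cover.

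**What to change.** Change Section 6 in one of two ways.

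- **(a) Derive the threshold.** Set it from the named benchmark for a fixed number of days from the start of consolidation, count relapse or death, and state the trigger probability at the benchmark and at a worse median. As an illustration at day 252 (exponential), for medians 13.8 / 11 / 6.9 months: 9 or more of 15 triggers 3.5% / 10% / 50% of the time, and 10 or more of 15 triggers 1.0% / 3.8% / 30%. The sponsor chooses the cutoff.
- **(b) Keep 80% as a lenient floor.** Say so, remove the claim that it is based on 13.8 months, and state its operating characteristics.

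In either case, name the dataset behind 13.8 months and say how it relates to the 11-month series in Section 1.2.

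The cost is wording only: no new patients or visits, since relapse and death dates are already needed for the planned curves. Option (a) brings more false futility than now, against 0.04% at 13.8 months and 0.2% at 11 months under the present rule. With 15 patients no cutoff separates well: 9 or more misses a halved median half the time, and 10 or more misses it 70% of the time. Option (b) leaves the rule as insensitive as it is, but openly so.

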The optimal consolidation regimen for older adults with AML in remission is unknown. The Cancer and Leukemia Group B (CALGB) defined repeated cycles of high dose cytarabine ($3\text{g}/\text{m}^2$ IV every 12hrs on days 1, 3, and 5, repeated every 28 days) as the standard consolidation regimen for younger patients with AML in remission, based on a randomized trial comparing four courses of cytarabine at one of three doses: $100 \text{ mg}/\text{m}^2$ of body-surface area per day for five days by continuous infusion, $400 \text{ mg}/\text{m}^2$ per day for five days by continuous infusion, or $3 \text{ g}/\text{m}^2$ in a 3-hour infusion every 12 hours (twice daily) on days 1, 3, and 5.¹⁵ The benefit of the high dose cytarabine consolidation predominantly extended to younger patients with core binding factor AML, although those with normal cytogenetics derived a lesser benefit¹⁶. The trial, however did not show a benefit for patients age > 60 , and only 29% of patients age > 60 received the intended cycles of high dose cytarabine. More recently, the German-Austrian AML Study Group carried out a clinical trial randomizing patients age 61 and older in first remission from AML after 2 cycles of induction and one consolidation, to either a second intensive consolidation (idarubicin $12\text{mg}/\text{m}^2$ IV days 1-3 and etoposide $100\text{mg}/\text{m}^2$ IV on days 1-5) or a 1-year oral maintenance therapy (idarubicin 5mg po on days 1, 4, 7, 10, and 13; etoposide 100mg po on days 1 and 13; repeated on day 29 for 12 courses). Analysis according to second randomization on an intention-to-treat basis revealed a statistically significant lower cumulative incidence of relapse ($P= 0.005$) in patients assigned to the intensive second consolidation compared to those assigned to the oral therapy. This translated into a statistically significant better survival ($P= 0.04$) with estimated median

survival times from second randomization of 22.3 and 14.3 months in the intensive vs. oral arm, respectively. However, this trial concluded that while a second intensive consolidation was beneficial, it could only be extended to the fraction of patients who could be randomized after remission¹⁷. **Thus better, more tolerable consolidation regimens are needed for older patients with AML who achieve remission.**

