2. STUDY OBJECTIVES

Primary Objectives:

- To assess the safety and tolerability of delivering omacetaxine for consolidation in adult patients age 55 and older with acute myelogenous leukemia (AML) in first complete remission following induction chemotherapy.
- To assess the safety and tolerability of delivering omacetaxine for maintenance in adult patients age 55 and older with acute myelogenous leukemia (AML) in first complete remission following 3 consolidation courses with omacetaxine.

Secondary Objectives:

- To assess the duration of remission.
- To evaluate disease-free survival (DFS).
- To evaluate overall survival (OS).
- To assess for minimal residual disease (MRD) during consolidation and maintenance therapy with omacetaxine.

3. RESEARCH DESIGN AND METHODS:

3.1 Patient Selection:

3.1.1 Inclusion Criteria:

1. Diagnosis of AML including de novo, secondary, or with an antecedent hematologic disorder [AHD] according to the World Health Organization (WHO) criteria²⁵ (**Appendix A**).
2. Age \geq 55 years.
3. Patient eligible for standard induction chemotherapy based on ECOG PS and vital organ function at the discretion of the treating physician.
4. Patients who received 1-2 cycles of hypomethylating therapy (decitabine azacitidine) are eligible.
5. Provide signed written informed consent.
6. Be able to comply with study procedures and follow-up examinations.
7. Be non-fertile or not pregnant or lactating & agree to use birth control during the study through the end of last treatment visit.
8. Adequate renal and hepatic function **at the time of second registration**:
 - a. Total bilirubin \leq 1.5 x institutional Upper Limit of Normal (ULN); and
 - b. Aspartate aminotransferase (AST) and alanine aminotransferase (ALT) \leq 2.5 x ULN; and
 - c. Serum creatinine \leq 1.2 times the upper limit of normal.
9. ECOG performance \leq 2 (**Appendix B**) **at the time of second registration**:
10. Patients with a history of carcinoma in remission, on no therapy or on hormonal therapy for the adjuvant treatment of breast carcinoma or prostate carcinoma are included in the study.

3.1.2 Exclusion Criteria:

1. Diagnosis of acute promyelocytic leukemia (APL, French-American-British [FAB] classification M3 or WHO classification of APL with t (15;17)(q22;q12), (*PML/RARA* and variants).
2. Prior treatment with omacetaxine
3. Relapsed or refractory AML.

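### Time to relapse is estimated by Kaplan-Meier with relapse as the only event, so relapse is overstated if a death in remission precedes later relapses

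*Combined protocol and SAP*

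**What the plan says.** Section 2 lists as a secondary objective: "To assess the duration of remission". Section 6 gives the method in one sentence: "Kaplan-Meier curves will be used to estimate the distribution of time to relapse, relapse free survival, and overall survival".

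Time to relapse has no definition of its own. The matching defined endpoint is remission duration, given in 3.3.2 and repeated in Appendix I: "Time from date of CR (or CRp, CRi) until disease relapse". Relapse-free survival (RFS), defined in the same list, adds death from any cause as an event.

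The plan gives no rule for a death in remission under time to relapse and names no competing-risk method. The transplant sentence in Section 6 covers overall survival (OS), event-free survival (EFS) and RFS, analysed with and without censoring at transplant. It does not mention time to relapse.

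**The concern.** Kaplan-Meier treats a censored patient as someone who could still have the event later. A patient who dies in remission cannot relapse. If that death is censored, the patient's weight passes to those still at risk, and each later relapse counts for more than it should. One minus the curve then no longer estimates the proportion of patients who relapse.

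The population is aged 55 and older, so deaths in remission are possible. RFS counts these deaths but does not separate them from relapses, so it cannot replace a relapse estimate. The post-remission trial in older patients described in section 1.3 reports its result as a "statistically significant lower cumulative incidence of relapse", and a one-minus-Kaplan-Meier figure would not be the same quantity.

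At stake is the accuracy of one descriptive estimate in a study that section 1.6 presents as preparatory: "This trial is a necessary step for an efficacy phase II trial".

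**Working it through.** The plan projects no relapse rate, so there is no figure of its own to reproduce. The check asks how large the excess could be.

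**Inputs**
- Median RFS m: 11 months (section 1.2) or 13.8 months (section 6, Futility). Both are used, only to set the scale.
- Scheduled treatment: 12 weeks of consolidation (Appendix E) plus 24 weeks of maintenance (Appendix F), so 36 × 7 / 30.4 = 8.3 months.
- Share s of first events that are deaths in remission: not given in the documents. Assumed 5% to 30%.

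**What the documents imply about s.** Section 1.2 says of the earlier series that "the median relapse-free survival was 11 months, and most patients died from relapsed leukemia". Section 1.6 says half of patients relapse within a year and 80% by 2 years. With constant hazards and m = 11, all RFS events (relapse plus death) reach 1 − exp(−ln2 × 12/11) = 53% at 12 months and 78% at 24 months. Relapse of 50% at 12 months leaves a death share of 1 − 50/53 = about 6%. Relapse of 80% at 24 months leaves no room for deaths. With m = 13.8 all events reach 45% and 70%, which again leaves no room. The section 1.6 figures are approximate, so they do not prove that s is small, but they point to the low end.

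**Formulas.** With H = ln2 × t/m:
- cumulative incidence of relapse = (1 − s)(1 − exp(−H))
- one minus Kaplan-Meier, deaths censored = 1 − exp(−(1 − s)H)

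For example, m = 11, t = 12 and s = 0.10 give H = 0.756. Cumulative incidence is 0.90 × 0.5305 = 47.7%, and one minus Kaplan-Meier is 1 − exp(−0.681) = 49.4%. The excess is 1.6 points.

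**Excess in percentage points**

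| s | 8.3 months, m = 11 / 13.8 | 12 months, m = 11 / 13.8 | 24 months, m = 11 / 13.8 |
|---|---|---|---|
| 5% | 0.5 / 0.3 | 0.8 / 0.6 | 2.2 / 1.6 |
| 6% | 0.5 / 0.4 | 1.0 / 0.7 | 2.6 / 2.0 |
| 10% | 0.9 / 0.6 | 1.6 / 1.1 | 4.2 / 3.2 |
| 20% | 1.6 / 1.1 | 2.9 / 2.0 | 7.8 / 5.8 |
| 30% | 2.1 / 1.4 | 4.0 / 2.7 | 10.7 / 8.0 |

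**Counts with 15 patients and 8 relapses, no other censoring before the last relapse.** The proportion relapsing is 8/15 = 53.3%.
- One death before the first relapse: 8/14 = 57.1% (+3.8).
- Two deaths before the first relapse: 8/13 = 61.5% (+8.2).
- One death after the second relapse: 1 − (13/15)(6/12) = 56.7% (+3.3).
- All deaths after the last relapse: 53.3% (no excess).

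The first two orderings are the least favourable for their number of deaths.

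**Sampling error.** With 15 patients and a 12-month relapse proportion of 32-48%, the standard error is √(p(1 − p)/15), about 12-13 points.

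**The case against.** The strongest case against is about size and consequence. Sections 1.2 and 1.6 suggest few deaths in remission. Scheduled assessments end at about 8 months of treatment, and the Synopsis has marrow examined afterwards only when clinically indicated. At that point the excess is at most about 2 points, well below the standard error. Censoring of deaths is also an inference from the method and the event definition; the text does not state it. All of this stands and limits the point. It does not justify the estimator, because the error is never negative and costs almost nothing to avoid.

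A reader might infer that relapse will be overstated by 3-11 points. That range needs a 10-30% share of deaths and follow-up to 24 months, and the documents establish neither.

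A reader might also infer that the futility rule is affected. It is not: it is a proportion "of those entering in CR relapse during consolidation/maintenance", which keeps deaths in the denominator. It also covers a different window from a curve that starts at remission, so the two could differ for that reason alone.

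Finally, OS is defined as "Time from entry onto trial until death from any cause", and the trial has two registrations. A reader might infer that the 15 omacetaxine patients gain guaranteed survival time by being timed from before induction. No passage specifies that pairing, and the interval between the registrations is not stated. What remains is an undefined term.

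**Conclusion.** The point holds as a minor correction to the analysis method. Followed as written, the plan would in effect censor deaths in remission and would overstate relapse whenever such a death precedes a later relapse. Where none does, the estimate is correct.

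Under assumed shares of 5-30% and constant hazards, the excess is up to about 2 points at 8 months and about 1-4 points at 12 months. At 24 months, if patients are followed that long, it is about 2-3 points at a share of 5-6% and up to about 11 points at 30%. The documents favour the low end.

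The affected outcome is secondary and descriptive. RFS, OS, the dose-limiting toxicity, feasibility and futility rules, and the sample size are unaffected. Section 1.6 says that this trial precedes a phase II trial; it does not say that the relapse curve will be used to plan it.

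**What to change.** In Section 6:
- Estimate relapse by cumulative incidence (Aalen-Johansen), with death in remission as the competing event.
- Report the cumulative incidence of death in remission beside it.
- Extend the planned analyses with and without censoring at transplant to time to relapse.
- Keep Kaplan-Meier for RFS and OS.

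The cost is about one sentence, plus confirmation that the case report forms distinguish deaths in remission from deaths after relapse; the documents do not list the form fields. No sample size, decision rule or treatment changes.

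As a wording note only, 3.3.2 and Appendix I could say which registration counts as trial entry for OS and EFS.
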